## **6.5. Drug Accountability**

Regulatory requirements stipulate accounting of all IMP (ie, ABI-H0731 and matching PBO) received by the study site. Records of IMP disposition must include the date received by the site, date administered, quantity administered, and the subject to whom the IMP was administered. The Investigator is responsible for the accountability of all IMP at his or her site. This includes all used and unused IMP bottles and unused IMP.

Each study site is to use an IMP accountability record to document IMP disposition. All items on this form are to be fully completed. The Sponsor or the CRO will confirm if the method of recording IMP accountability by the site and the location of IMP records at the site is appropriate.

Each time designated site personnel dispense IMP for a subject, he or she is to record the date dispensed, the quantity of IMP dispensed, and his or her initials. Study site personnel are to monitor the inventory of clinical supplies and maintain a count of all used and unused IMP. The site monitor will review the IMP accountability records during monitoring visits. The site pharmacist or designated staff member will keep accurate records of IMP dispensation routinely during the study ([Section 7](#); [Appendix 1](#)).

NrtI accountability will be captured by the subjects in dosing diaries.

## **6.6. Study Drug Administration and Compliance**

Subjects participating in this study will receive ABI-H0731 or PBO in addition to standard-of-care treatment with a NrtI. ABI-H0731 (3 × 100 mg tablets) or PBO tablets should be administered as a single dose, once daily. Subjects will self-administer assigned treatment and should be instructed to take ABI-H0731 or PBO at the same time of the day with the possible exception of in-clinic visit days. To monitor IMP compliance and to facilitate IMP accountability at the study site, subjects will be required to record each dose/quantity of tablets taken of ABI-H0731 or matching PBO in a dosing diary provided to the subject at visits shown in the Schedule of Assessments ([Appendix 1](#)). Subjects will also be asked to return used bottles and any unused IMP at study visits for accountability and compliance assessment at each visit. Returned IMP will be counted and reconciled against the diary entries by study site personnel preferably in the presence of the subject. Subjects who forget to return IMPs at a given visit will be asked to return them at the next study visit. The IMP dosing dates and time for doses given at the PK collection study visits will be entered in the subject's eCRF.

For assessment of compliance to the NrtI (NIMP) regimen, subjects will be provided dosing diaries at each study visit and will be asked to record the dosing dates, times, and quantity for NrtI administration. The dosing dates and time of NrtI at the PK collection study visits will be entered in the subject's eCRF by study site personnel.

Additional information concerning study treatments and the management of missed or incorrect doses is provided in the Study Pharmacy Manual.

## **6.7. Return or Disposal of Study Drug**

Procedures for the return of IMP or provisions for onsite destruction (where approved prospectively by the Sponsor) are described separately in the Study Pharmacy Manual.

## 7. STUDY PROCEDURES

The schedule of assessments to be conducted in the study is provided in tabular form in [Appendix 1](#).

### 7.1. Subject Enrollment and Treatment Assignment

Following provision of informed consent and completion of all Screening and Day 1 assessments, if a subject meets all protocol eligibility requirements the Investigator or designee will randomize the subject using the IRT system described in [Section 6.1.1](#). Protocol waivers will not be granted.

#### 7.1.1. Screen Failures

Screen failures are defined as subjects who consent to participate in the clinical study but are not subsequently randomized to study treatment. Minimal information to be retained on all screen failures includes demography, screen failure details, eligibility criteria, and any SAE information (if applicable).

Individuals who do not meet the protocol eligibility criteria for participation in this study (ie, screen failures) may not be rescreened, however, a single retest for a laboratory parameter(s) is permitted if there is considered to be a specific issue related to the collection, shipping, processing, or analysis of a sample (eg, receipt of a hemolyzed sample at the testing laboratory, or samples received by the testing laboratory outside of the acceptable temperature range, or resolved intercurrent illness).

### 7.2. Screening Assessments (Day -45 to Day -1)

It is recommended, though not mandated, that invasive procedures, such as a liver biopsy (if required) are not conducted until it has been determined that the subject is broadly eligible for study participation.

The following Screening assessments must be completed within 45 days of the scheduled Day 1 visit:

- Obtain written informed consent
- A separate consent is required for the subject to provide an optional pharmacogenomic sample
- Record demographics and medical history, including HBV history
- Measure height and body weight
- Vital signs (temperature, heart rate, respiration rate, and blood pressure)
- Complete physical examination (excluding breast and genitalia, unless indicated)
- 12-lead ECG
- Review of concomitant medications
- Review of AEs occurring after provision of informed consent
- Liver staging (as required per inclusion criteria, ie, fasting FibroScan)
- Laboratory analyses (additional details are provided in the Laboratory Manual):

- Safety labs: chemistry, hematology, coagulation, serum AFP, follicle-stimulating-hormone (FSH) (females only), HbA1c, serum pregnancy test for females of child-bearing potential only, urinalysis, urine drug test ([Appendix 2](#))
- Virology: HBV DNA, HBV pgRNA, HBsAg, HBeAg, HBsAb, HBeAb, sample for HBV sequencing and HBV nucleic acids, HIV Ab, HCV Ab, HDV Ab, HAV (immunoglobulin M [IgM]), HEV (IgM) (see [Appendix 2](#))
  - A second HBV DNA sample will be drawn approximately 10 to 14 days after the initial Screening Visit. If the results from the 2 HBV DNA samples indicate a numeric decline in HBV DNA during the Screening assessment period, then a third sample at least a week later will be collected for Sponsor review and approval prior to randomization.
- HBV sequencing: a blood sample for sequencing of the HBV polymerase coding region will be collected and analyzed. The presence of specific base substitutions which may confer reduced susceptibility to NrtIs would exclude subjects from participating in the study (see [Appendix 2](#))
- HBV immunology: whole blood sample for collection of peripheral blood mononuclear cells (PBMCs) followed by serum cytokine sample collection for immunologic testing at selected sites only ([Appendix 2](#))

### 7.3. Day 1

The following assessments must be completed at Day 1:

- Update medical history, including HBV history
- Measure body weight
- Vital signs (temperature, heart rate, respiration rate and blood pressure)
- Complete physical examination (excluding breast and genitalia, unless indicated)
- 12-lead ECG
- Review concomitant medications
- Review AEs
- Confirm subject eligibility
- Complete randomization
- Laboratory analyses (additional details are provided in the Laboratory Manual):
- Safety labs: chemistry, hematology, coagulation, urine pregnancy test for females of child-bearing potential only, urinalysis, urine drug test (see [Appendix 2](#))
- Virology: HBV genotype, HBV DNA, HBV pgRNA, HBsAg, HBeAg, HBcrAg, HBsAb, HBeAb, sample for HBV sequencing and HBV nucleic acids (see [Appendix 2](#))
- Immunology (For subjects who provided PBMCs at Screening at selected sites ONLY): PBMCs collection followed by serum cytokine sample and PaxGene® DNA and PaxGene® RNA sample collection (see [Appendix 2](#)).

- PK samples: predose samples for ABI-H0731 or PBO and NrtI. Postdose samples for ABI-H0731 and NrtI between 2 and 4 hours following study drug administration (see [Section 7.10](#))
- Pharmacogenomic Sample: Optional and only collected in subjects who provide additional informed consent.
- Dispense dosing diary
- ABI-H0731 or PBO dispensation
- ABI-H0731 or PBO administration
- NrtI administration

#### **7.4. Study Weeks 2 Through 48**

The following assessments are performed at Study Weeks 2, 4, 8, 12, 16, 20, 24 and then every 4 weeks thereafter through Week 48 (inclusive) unless otherwise indicated. Subjects who discontinue treatment before Week 48 should immediately undergo the assessments listed for the Premature Termination visit and then continue the scheduled follow-up assessment. A visit window of  $\pm 3$  days is applied to each visit through Week 44. A visit window of -3 days is applied to Week 48. ([Appendix 1](#))

- Measure body weight (Week 48 only)
- Vital signs (temperature, heart rate, respiration rate, and blood pressure)
- Complete physical examination (excluding breast and genitalia, unless indicated; Week 48 only)
- Symptom-directed physical examination (not at Week 48)
- 12-lead ECG (Weeks 12, 24, 36, and 48 only)
- Review concomitant medications
- Review AEs
- Laboratory analyses (additional details are provided in the Laboratory Manual):
- Safety labs: chemistry, hematology, coagulation (not at Week 2), urinalysis (not at week 2), urine pregnancy test for females of child-bearing potential only (see [Appendix 2](#))
- Virology: HBV DNA, HBV pgRNA, HBsAg (not at Week 2), HBeAg (not at Week 2), HBcrAg (not at Week 2), HBsAb and HBeAb (Weeks 12, 24, and 48 only), sample for HBV sequencing and HBV nucleic acids (Weeks 20 to 44 and Week 48) (see [Appendix 2](#))
- Immunology (For subjects who provided PBMCs at Screening at selected sites ONLY): PBMCs collection followed by serum cytokine sample collection at Weeks 2, 4, 12, 24, 36, and 48 (see [Appendix 2](#))
- PK samples: samples for ABI-H0731 or PBO and NrtI may be collected from 2 to 4 hours postdose on Day 1, between 30 min to 2 hours postdose at Weeks 2, 8, 12, 24, and 28, and between 4 and 6 hours postdose at Weeks 16 and 20. Predose samples for ABI-H0731 or PBO and NrtI will be collected at Week 4, and Week 48 only (see [Section 7.10](#))
- Review dosing diary and assess ABI-H0731 or PBO accountability

- ABI-H0731 or PBO dispensation
- ABI-H0731 or PBO administration
- NrtI administration
- Dispense dosing diary

## 7.5. Study Weeks 52 to 96

The following assessments are performed every 4 weeks unless otherwise indicated. A visit window of  $\pm 5$  days is applied from Weeks 52 through 96.

- Measure body weight (Week 96 only)
- Vital signs (temperature, heart rate, respiration rate and blood pressure)
- Complete physical examination (excluding breast and genitalia, unless indicated; Week 96 only)
- Symptom-directed physical examination (Weeks 52 to 92 only)
- 12-lead ECG (Week 96 only)
- Review concomitant medications
- Review AEs
- Laboratory analyses (additional details are provided in the Laboratory Manual):
- Safety labs: chemistry, hematology, coagulation, urinalysis, urine pregnancy test for females of child-bearing potential only (see [Appendix 2](#))
- Virology: HBV DNA, HBV pgRNA, HBsAg, HBeAg, HBcrAg, HBsAb, and HBeAb (Weeks 72 and 96 only), sample for HBV sequencing and HBV nucleic acids (see [Appendix 2](#))
- Immunology (For subjects who provided PBMCs at Screening at selected sites ONLY): PBMCs collection followed by serum cytokine sample collection at Weeks 60, 72, 84, and 96 (see [Appendix 2](#)). Additionally, these subjects will provide PaxGene® RNA sample at Week 96 only.
- Review dosing diary
- Assess ABI-H0731 accountability (final ABI-H0731 accountability performed at Week 96)
- ABI-H0731 dispensation (final ABI-H0731 dispensation performed at Week 92)
- ABI-H0731 administration
- NrtI administration
- Dispense dosing diary

## 7.6. Follow-up Assessments

All subjects who prematurely discontinue treatment or complete treatment per protocol will enter a 24-week follow-up period during which they will have the following assessments performed between

4 weeks and 20 weeks and at 24 weeks ( $\pm 5$  days) after the last dose of study drug unless otherwise stated. Subjects will remain on standard of care NrtI during the follow-up period:

- Measure body weight (24 Weeks post only)
- Vital signs (temperature, heart rate, respiration rate and blood pressure)
- Complete physical examination (24 Weeks post only)
- Symptom-directed physical examination (not at 24 Weeks post)
- 12-lead ECG (24 Weeks post only)
- Review concomitant medications
- Review AEs
- Laboratory analyses (additional details are provided in the Laboratory Manual):
- Safety labs: chemistry, hematology, coagulation, urinalysis (4 Weeks post and 24 Weeks post only), urine pregnancy test (only at 4 Weeks post and for female of child-bearing potential) (see [Appendix 2](#))
- Virology: HBV DNA, HBV pgRNA, HBsAg, HBeAg, HBcrAg, HBsAb, and HBeAb (24 Weeks post only), sample for HBV sequencing and HBV nucleic acids (see [Appendix 2](#))
- Immunology (For subjects who provided PBMCs at Screening at selected sites ONLY): PBMCs collection followed by serum cytokine sample collection at 4-, 12-, and 24-Weeks post (see [Appendix 2](#)). Additionally, these subjects will also provide a PaxGene® RNA sample at 24 Weeks post only.
- PK sample: samples for ABI-H0731 or PBO and NrtI collected at 4 Weeks post. See [Section 7.10](#) for additional information on PK sampling.
- Review dosing diary for NrtI ONLY
- NrtI administration at 4 Weeks post ONLY
- Dispense dosing diary (EXCEPT at 24 Weeks Post)

## 7.7. **Unscheduled Visit**

An unscheduled visit may be performed at any time at the discretion of Investigator in order to further evaluate a subject. The specific assessments to be performed at these visits would be determined by the Investigator according to nature of the subject specific follow-up required, however at a minimum the assessments would include the following:

- Vital signs (temperature, heart rate, respiration rate and blood pressure)
- Symptom-directed physical examination
- Review concomitant medications
- Review AEs
- Laboratory analyses (additional details are provided in the Laboratory Manual):

- Safety labs: chemistry, hematology, coagulation, urinalysis, urine drug test, urine pregnancy test for females of child-bearing potential only (see [Appendix 2](#))
- Virology: HBV DNA, HBV pgRNA, HBsAg, HBeAg, HBcrAg, sample for HBV sequencing, and HBV nucleic acids (see [Appendix 2](#))
- PK samples: samples for ABI-H0731 or PBO and NrtI. See [Section 7.10](#) for additional information on PK sampling.

Assessments performed should be documented in the subject's source documentation. Clinical laboratory assessments should be conducted through the central laboratory.

## 7.8. Premature Termination Visit

Should a subject prematurely discontinue treatment ([Section 7.9.1](#)) or discontinue from the study ([Section 7.9.2](#)), a Premature Termination visit should be scheduled. While the Investigator may include additional assessments and evaluations determined by the status of the individual subject, at the minimum, the following assessments should be performed as soon as feasibly possible:

- Vital signs (temperature, heart rate, respiration rate, and blood pressure)
- Complete physical examination (excluding breast and genitalia unless indicated)
- 12-lead ECG
- Review concomitant medications
- Review AEs
- Laboratory analyses (additional details are provided in the Laboratory Manual):
- Safety labs: chemistry, hematology, coagulation, urinalysis, urine drug test, urine pregnancy test for females of child-bearing potential only (see [Appendix 2](#))
- Virology: HBV DNA, HBV pgRNA, HBsAg, HBeAg, HBcrAg, HBsAb, and HBeAb, sample for HBV sequencing and HBV nucleic acids (see [Appendix 2](#))
- PK samples: samples for ABI-H0731 or PBO and NrtI. See [Section 7.10](#) for additional information.
- Immunology (For subjects who provided PBMCs at Screening at selected sites ONLY): PBMCs collection followed by serum cytokine and PaxGene® RNA sample collection (see [Appendix 2](#)).
- Review dosing diary and assess IMP accountability (if applicable)

## 7.9. Discontinuation

A subject may withdraw from the study at any time at his/her own request or may be withdrawn at any time at the discretion of the Investigator or Sponsor for safety, behavioral, compliance, or administrative reasons. This is expected to be uncommon. At the time of discontinuation from the study, if possible, a Premature Termination visit should be conducted ([Section 7.8](#)). If the subject withdraws consent for disclosure of future information, the Sponsor may retain and continue to use any data collected before such a withdrawal of consent. If a subject withdraws from the study, he/she may

request destruction of any samples taken and not tested, and the Investigator must document this in the site study records.

### **7.9.1. Discontinuation from Treatment**

If an individual subject is, in the judgement of the Investigator, not satisfactorily tolerating study drug treatment due to AEs, then in consultation with the Sponsor, the subject may discontinue treatment with ABI-H0731 or PBO. NrtI may be continued at the discretion of the Investigator. Discontinuation from treatment does not mean discontinuation from the study. Subjects who prematurely discontinue treatment should immediately undergo the assessments listed for the Premature Termination visit ([Section 7.8](#)) and then continue scheduled follow-up assessments ([Section 7.6](#)).

In this study, subjects will be closely monitored for ALT elevations and declining hepatic function. Procedures to be followed for these subjects are described in [Section 9.4](#). Study treatment will be discontinued in subjects with confirmed evidence of declining hepatic function during treatment, a Premature Termination visit ([Section 7.8](#)) will be completed, and subjects will subsequently undergo the follow-up assessments described in [Section 7.6](#).

Any subjects negative by urine pregnancy test at Baseline (Day 1) who are subsequently found to be positive on serum pregnancy test should immediately discontinue treatment with ABI-H0731 or PBO. NrtI may be continued if indicated based on Investigator judgment in accordance with local practice and the approved NrtI package insert. These subjects may be replaced at the discretion of the Sponsor.

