## 1. SYNOPSIS

**Protocol Number:** ABI-H0731-205

**Title:** A Phase 2a, Multi-Center, Single-Blind, Placebo-Controlled Study Evaluating Treatment Intensification with ABI-H0731 in Subjects with Chronic Hepatitis B Infection on Nucleos(t)ide Reverse Transcriptase Inhibitors

**Phase:** 2a

**Number of Subjects:** Approximately 40

**Study Duration:** Up to 45 days for Screening, 96 weeks treatment, and 24 weeks of follow-up

**Rationale:** Chronic hepatitis B infection (CHB) is a major cause of liver-related morbidity and mortality worldwide. While standard-of-care nucleos(t)ide reverse transcriptase inhibitors (NrtI) targeting the hepatitis b virus (HBV) polymerase are able to suppress viral replication (ie, HBV DNA below the limitation of quantification [LLOQ]), around 30% of hepatitis B 'e' antigen (HBeAg) positive patients and 10% of HBeAg negative patients have only a partial virologic response and are not able to reach this goal by treatment Week 48. Combination approaches are needed to provide adequate viral suppression in these patients. ABI-H0731 is a direct-acting antiviral agent targeting the HBV core protein. Through this mechanism, ABI-H0731 interferes with multiple steps in the viral lifecycle including capsid disassembly and HBV DNA delivery to the nucleus, HBV pregenomic RNA (pgRNA) encapsidation, capsid assembly and HBV DNA recirculation preventing de novo cccDNA establishment. It is anticipated that ABI-H0731 administered in combination with NrtI will be safe and result in complete viral suppression in subjects unable to attain this status on NrtI alone. This Phase 2a study will explore the safety of ABI-H0731 when added to NrtI and evaluate the antiviral activity of the ABI-H0731+NrtI combination as measured by the proportions of partially virologically suppressed subjects achieving HBV DNA <LLOQ at Week 48.

**Target Population:** Male or female, aged 18 to 65 years (inclusive), with HBeAg positive or HBeAg negative CHB and no evidence of cirrhosis or end-stage liver disease who are not adequately suppressed on NrtI therapy.

**Test Product:** 300 mg ABI-H0731 as three 100 mg tablets and NrtI, oral administration

**Reference Product:** ABI-H0731-matching placebo (PBO) (as 3 tablets) and NrtI, oral administration

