## **6.3. Description and Handling of NrtI (Non-Investigational Medicinal Product)**

All subjects will enter the study receiving standard-of-care NrtI monotherapy of either ETV, TDF or TAF. The NrtIs used by subjects in this study are designated as non-investigational medicinal products (NIMP) (background therapy). Subjects taking a NrtI other than ETV, TDF, or TAF are excluded from study participation. Subjects will continue to administer their same standard-of-care NrtI used prior to and during Screening and continue for the entire duration of the study including follow-up. If a subject's access to concurrent standard of care NrtI therapy should change while on-study, then the Investigator should first contact the Sponsor and/or authorized Medical Monitor to discuss the case-

Details describing the packaging, labelling, storage and handling of the NrtI are described in the respective package insert.

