#### **8.7. Pregnancy**

##### **8.7.1. Female subjects who become pregnant**

Any female subject who becomes pregnant while participating in the study will discontinue the study drug(s) immediately.

The Investigator will collect pregnancy information on any female subject who becomes pregnant while participating in this study, including the 24-week follow-up period. The initial information will be recorded on the Pregnancy Reporting form and submitted to the CRO Pharmacovigilance group within 24 hours of learning of a subject’s pregnancy. Refer to the Study Reference Manual for contact information for reporting a pregnancy.

The subject will be followed to determine the outcome of the pregnancy. The Investigator will collect follow-up information on the subject and the neonate and the information will be forwarded to the Sponsor. Generally, follow-up will not be required for longer than 6 to 8 weeks beyond the estimated delivery date. Any termination of pregnancy will be reported, regardless of fetal status (presence or absence of anomalies) or indication for the procedure.

While pregnancy itself is not considered to be an AE or SAE, any pregnancy complication or elective termination of a pregnancy for medical reasons will be reported as an AE or SAE. A spontaneous

abortion (occurring at <22 weeks gestational age) or still birth (occurring at >22 weeks gestational age) is always considered to be an SAE and will be reported as such.

Any post-study pregnancy related SAE considered reasonably related to the study drug(s) by the Investigator will be reported to the Sponsor. While the Investigator is not obligated to actively seek this information in former study subjects, he or she may learn of an SAE through spontaneous reporting.

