- If ALT is rising at the confirmatory visit, subjects should return for an **Unscheduled Visit** every 2 to 5 days until the ALT elevation has stabilized. At these visits the following laboratory tests will be performed: ALT, AST, total bilirubin (if total bilirubin is elevated, reflex to Direct Bilirubin), serum albumin, INR, HBV DNA, and quantitative HBV serologies (HBeAg [reflex qualitative HBeAg if quantitative HBeAg is negative] and HBsAg [reflex qualitative HBsAg if quantitative HBsAg is negative]). Subjects whose ALT has stabilized should continue to be monitored weekly (or more frequently, as deemed necessary by the treating physician) until ALT values return to normal or Baseline levels.
  - Subjects with an ALT elevation without declining hepatic function and without contraindications should discontinue study drug if the ALT remains persistently elevated for >4 weeks
- Subjects with confirmed ALT elevation with evidence of declining hepatic function should be discontinued from study treatment. This is defined as:
  - ALT elevation  $\geq 2 \times$  Baseline or nadir and  $> 2 \times$  ULN AND
    - Direct bilirubin increase to  $\geq 2 \times$  Baseline and  $\geq 2 \times$  ULN OR
    - Albumin decline  $\geq 0.5$  g/dL OR INR  $> 2 \times$  Baseline OR
    - Symptoms of liver inflammation (eg, fatigue, weakness, lack of appetite, nausea, vomiting, jaundice, or discolored feces)
- Subjects with evidence of declining hepatic function should return for an **Unscheduled Visit** every 2 to 5 days until the relevant laboratory values stabilize. Subjects whose hepatic function has stabilized should continue to be monitored weekly (or more frequently as deemed necessary by the Investigator) until the relevant laboratory values return to normal or Baseline.
- **Post-treatment ALT Elevation**

Following cessation of study drug treatment under this protocol all subjects will be closely followed for ALT elevations and/or signs of potential decline in hepatic function. This applies to all subjects whether they prematurely discontinue study drug or complete the study per protocol. Any subject with a post-treatment ALT elevation without evidence of declining hepatic function or a post-treatment ALT elevation with evidence of declining hepatic function as defined above, will be evaluated as noted above.

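### Section 7.9.1 makes background NrtI optional after an early stop, while 6.3, 7.6 and Appendix 1 say it continues; the hepatic stopping rule does not define what is stopped

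*Combined protocol and SAP*

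**What the plan says.** **NrtI after an early stop.** Section 7.9.1, first paragraph, deals with subjects who do not tolerate treatment because of adverse events. ABI-H0731 or placebo may be stopped, and "NrtI may be continued at the discretion of the Investigator". The third paragraph, on pregnancy, stops ABI-H0731 or placebo and again leaves NrtI to the investigator's judgment, in line with local practice and the label.

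Section 6.3 says subjects keep the NrtI they were on at Screening and "continue for the entire duration of the study including follow-up". The only departure it foresees is a change in access to NrtI, which goes to the Sponsor or Medical Monitor. Section 7.6 says "All subjects who prematurely discontinue treatment or complete treatment per protocol will enter a 24-week follow-up period" and then "Subjects will remain on standard of care NrtI during the follow-up period". Appendix 1 footnote 16 also has NrtI continuing throughout follow-up.

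**What the stopping rules stop.** For worsening liver function, the second paragraph of 7.9.1 reads "Study treatment will be discontinued in subjects with confirmed evidence of declining hepatic function during treatment". Section 9.4 says that subjects with a confirmed ALT elevation and "evidence of declining hepatic function should be discontinued from study treatment". Neither mentions NrtI. On pregnancy, section 8.7.1 says the subject "will discontinue the study drug(s) immediately", and Appendix 1 footnote 11 simply says treatment stops.

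**How the products are described.** The Synopsis gives the Test Product as "300 mg ABI-H0731 as three 100 mg tablets and NrtI, oral administration". Section 6.3 classes NrtI as non-investigational background therapy.

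**The concern.** A subject who stops ABI-H0731 or placebo for an adverse event is told by 7.9.1 that NrtI is optional and by 7.6 that it goes on. Two sites could handle the same case differently, and each could cite the protocol. The hepatic rule raises a related question: a site must work out for itself whether stopping *study treatment* includes the background antiviral. It applies to subjects with worsening liver function, so its scope should not be left to inference.

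The statistical stake is interpretation. HBV DNA and ALT are the quantities the trial measures, and NrtI acts on them. Early stoppers remain in the as-randomized Full Analysis Set and in 24 weeks of follow-up. If some also stop NrtI, their later HBV DNA and ALT values mix withdrawal of background therapy with withdrawal of ABI-H0731.

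**Working it through.** The protocol has no figure to reproduce: section 10.1 says the sample size has no statistical basis. The check is a comparison of text.

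| Place | Situation | What stops | NrtI |
|---|---|---|---|
| 6.3 | All subjects | – | Continues to end of study |
| 7.6 | Early stoppers and completers | – | Continues in follow-up |
| App. 1, fn 16 | Follow-up | – | Continues in follow-up |
| 7.9.1, para 1 | Adverse events | ABI-H0731 or placebo | Optional |
| 7.9.1, para 2 | Declining hepatic function | *Study treatment* | Not mentioned |
| 9.4 | Declining hepatic function | *Study treatment* | Not mentioned |
| 9.4 | ALT elevated for more than 4 weeks | *Study drug* | Not mentioned |
| 7.9.1, para 3 | Pregnancy | ABI-H0731 or placebo | Optional |
| 8.7.1 | Pregnancy | *Study drug(s)* | Not mentioned |
| App. 1, fn 11 | Positive serum test after negative urine test | *Treatment* | Not mentioned |

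**Step 1: can 7.9.1 be read as an exception to 7.6?** No. Section 7.6 names early stoppers among those it covers, and 7.9.1 itself sends them to 7.6. Two paragraphs make NrtI optional, and three places make it unconditional for the same people.

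**Step 2: do the hepatic rules name the product?** In 0 of 3. *Study treatment* is never defined. Three places allow it to include NrtI: the Synopsis Test Product line, section 4.3 (headed Study Treatments, covering both products) and section 6.1.2 (which gives the assignments as placebo plus NrtI or ABI-H0731 plus NrtI). Where the authors meant the investigational product alone, they could say so, as in 6.1.3 on unblinding and in the paragraphs of 7.9.1 on either side of the hepatic one.

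**Step 3: do the pregnancy rules name the product?** In 1 of 3. Section 7.9.1 does; 8.7.1 and footnote 11 do not. Section 8.7.1 also counts the 24-week follow-up as participation. By then ABI-H0731 has stopped, so its instruction to stop *study drug(s)* has no clear object.

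**Step 4: size.** With 20 subjects planned per arm (6.1.1), one subject is 1/20 = 5 percentage points of an arm's Week 48 response rate. That is a ceiling per subject: NrtI must actually stop, and responder status must change as a result. The SAP (section 1) reports 2 subjects randomized at early termination; SAP sections 3 and 6 plan listings only and no formal efficacy analysis. The effect on any efficacy estimate is therefore nil.

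**The case against.** **The term *study drug* is reasonably clear from use.** Appendix 1 footnote 18 writes study drug and NrtI as separate items. Section 7.6 counts follow-up from the last dose of study drug while NrtI goes on. Section 9.4 speaks of study drug having ceased in completers, who remain on NrtI. SAP 7.1.3, on relationship to study drug, uses a form item that asks about ABI-H0731 or placebo. This stands. It does not settle *study treatment*, the term in the declining-function rule.

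**A reader might infer that the hepatic rule contradicts 7.6.** It does not. It sends subjects to 7.6, where NrtI status is stated, and the discretion sentence belongs to the adverse-event paragraph. The hepatic defect is an undefined term. The monitoring in 9.4 applies regardless.

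**A reader might infer that the pregnancy rules never say which drug stops.** Section 7.9.1 does say. The defect is that 8.7.1 and footnote 11 do not match it, and that its optional NrtI conflicts with 6.3, 7.6 and footnote 16.

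**A reader might multiply the 5 points by several assumed stoppers per arm.** The documents do not support that as an effect. Subjects enter unsuppressed after more than 12 months of NrtI, so a stopper may well be a non-responder whether or not NrtI continues. Follow-up lasts 24 weeks after the last dose, so someone stopping before about Week 24 has no scheduled Week 48 sample and would be imputed under 10.6. The only stopping rate given is from Study 211, 2 of 92 over 24 weeks. Scaled crudely, 2/92 × 20 × 48/24 ≈ 0.9 per arm, and that was a different population.

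**NrtI dates are partly captured already.** Section 6.4 puts medication start and stop dates in source records, diaries cover NrtI, and SAP 7.4.2 lists medications by subject. This largely stands. However, 6.6 calls for NrtI dosing dates in the eCRF only at PK visits, and the SAP does not tie an NrtI stop to the virology or laboratory listings.

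**Conclusion.** The point holds in two parts. First, the protocol gives conflicting instructions on NrtI after ABI-H0731 or placebo is stopped for adverse events or pregnancy: optional in 7.9.1, unconditional in 6.3, 7.6 and footnote 16. Second, the declining-hepatic-function rule uses an undefined term that can be read to include NrtI, and 8.7.1 and footnote 11 are not aligned with 7.9.1 on pregnancy.

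This is an error of wording and should be corrected, because it concerns handling of subjects with adverse events or worsening liver function and the reading of their HBV DNA and ALT. The text findings need no assumption; different handling between sites is an inference from them. With 2 subjects and listings only, what remains for the data is that a listed value taken after ABI-H0731 or placebo stops cannot be interpreted without knowing whether NrtI was still being taken.

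**What to change.** - Reconcile 7.9.1, paragraphs 1 and 3, with 6.3, 7.6 and Appendix 1 footnote 16, so that one statement governs NrtI after any early stop. Which rule that should be is for the sponsor and investigators.
- Define *study drug* and *study treatment* once. The first also sets the SAP's 28-day window for treatment-emergent events (SAP 7.1.5.1).
- Name the intended product or products in 7.9.1 paragraph 2, 9.4, 8.7.1 and footnote 11.
- Make any NrtI stop date identifiable in the by-subject virology and laboratory listings, so that later HBV DNA and ALT values are not read as the effect of stopping ABI-H0731.

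The cost is wording in a handful of sections and, for the listings, one date carried across from the medication records. No visits, samples or subjects are added.
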